9.1 Data handling for Cohort A Primary Analysis

By the nature of Cohort A primary analysis, Cohort A data after Week 16 may be incomplete and subject to further change. Cohort A data after Week 16 will not be used for summary statistics, statistical analyses, listings or imputations, with the exception of all available adverse events and treatment exposure data that will be included in the analysis.

9.2 Definition of Baseline and Change from Baseline

In general, the last non-missing measurement prior to the first administration of study intervention will serve as the baseline measurement. In case a participant was randomized but did not receive the study intervention, the last non-missing measurement prior to the date of randomization will be used as baseline value.

For all efficacy endpoints of Section 14, only assessment date, but not the hours, will be used in the derivation of baseline value, i.e., an assessment collected the same day but after the first administration of study intervention will be considered for the derivation of baseline value.

INFORMATION

For other endpoints, if an assessment which is planned to be performed before randomization or study intervention per protocol is performed on the same day as the randomization or start of study intervention, respectively, but the assessment time is not available, it will be assumed that it was performed prior and will be considered for derivation of baseline.

Absolute and percent changes from Baseline are defined as

absolute change = visit value – baseline value

percent change = 100 * (visit value – baseline value) / baseline value

9.3 Study Day / Study Intervention Day

Day 1 is the day of first dose of study intervention, the day before is Day -1 (no Day 0 is defined). Study day / Study intervention day is defined relative to Day 1.

9.4 Definition of Duration and 'Time Since' Variables

Durations in days will be calculated by the difference of start and stop date + 1 (e.g., AE duration (days) = stop date - start date + 1) if not otherwise specified.

The time since an event (e.g., time since documented diagnosis) will be calculated as reference date minus date of event.

9.5 Conversion Factors

The following conversion factors will be used:

- 1 week = 7 days, 1 month = 30.4375 days, 1 year = 365.25 days
- 1 kg = 2.20462 lbs
- 1 cm = 0.39370 in
- From °F to °C: (°F 32) / 1.8000

9.6 Date of Last Contact

The date of last contact will be derived for all participants using the latest complete date prior to or at the data cut-off date among the following:

CONFIDENTIAL

INFORMATION

- AE start and end dates
- Date of last study intervention
- Date for any study assessments
- Date of study completion/discontinuation
- Date of death

Only dates associated with actual examinations of the participant reported in the eCRF will be used in the derivation. Dates associated with a technical operation unrelated to participant status such as the date a blood sample was processed will not be used.

9.7 Time Window

Unless otherwise specified, study measurements will be assigned an analysis visit based on their actual assessment date as described in the table below.

Analysis Visit	Target Day	Window Range
Day 1	1	1
Week 2 Day 15	15	> 1 – 21
Week 4 Day 29	29	22 – 42
Week 8 Day 57	57	43 – 70
Week 12 Day 85	85	71 – 98
Week 16 Day 113	113	99 – 126
Week 20 Day 141	141	127 – 154
Week 24 Day 169	169	155 – 176
Safety Follow-up Visit Week 26 Day 183	183	≥ 177

For the Cohort B final analysis, the following table will be used:

Analysis Visit	Target Day	eCRF visit	Window Range
Day 1	1	Any	1
Week 2 Day 15	15	Any	> 1 – 21
Week 4 Day 29	29	Any	22 – 42
Week 8 Day 57	57	Any	43 – 70
Week 12 Day 85	85	Any	71 – 98
Week 16 Day 113	113	Any	99 – 126
Week 20 Day 141	141	Any	127 – 154
Week 24 Day 169	169	Any	155 – 176
		Any apart from Safety Follow-up visit	177 – 182
Safety Follow-up Visit Week 26 Day 183	183	Safety Follow-up visit	177 – 182
		Any	> 182

In case multiple assessments are assigned to the same window, the closest value to the target day will be considered for analysis. If two values are observed with the same distance to the target day (one before and one after), then the earlier value will be used for analysis.

In case several time points are scheduled on a same day, specifications will be provided for the related parameters. For parameters not expected to be collected at each visit, visit windows will be combined. As an example, if a parameter is not measured at Week 2, the Week 4 visit window will extend from > 1 to 42.

CONFIDENTIAL

INFORMATION

Definition of On-treatment Period 9.8

The on-treatment period is defined as the time from the first dose of study intervention to the date of last contact.

9.9 **Exposure time**

Duration of exposure to study intervention = end date – date of first dose of study intervention +1, where:

• end date is the date of last dose of study intervention.

9.10 **Imputation of Missing Data**

Disease history:

Incomplete dates for documented diagnosis of CLE or SLE will be imputed as follows:

- If the day is missing, it will be imputed to the 1st day of the month.
- If both day and month are missing and the year is available, the month and day will be imputed as January 1st.
- If the date is completely missing, no imputation will be performed.

Exposure:

In case the start date of study intervention is missing, it is assumed that the first dose of study intervention is given at the randomization date. The randomization date will replace incomplete dates of the first dose of study intervention.

Adverse events:

Incomplete AE-related dates will be imputed as follows:

- In case the onset date is missing completely or missing partially but the onset month and year, or the onset year are equal to the start of study intervention then the onset date will be imputed by the minimum of start of study intervention and AE resolution date (if not missing).
- In all other cases, the missing onset day or missing onset month will be imputed by 1.
- Incomplete stop dates will be imputed by the last day of the month (if day is missing only), if not resulting in a date later than the date of participant's death. In the latter case, the date of death will be used to impute the incomplete stop date.
- In all other cases, the incomplete stop date will not be imputed.

Previous and concomitant medication:

Incomplete previous/concomitant medication start and stop dates will be imputed as presented in Table 1Table 1.

For the derivation of previous and concomitant medications, the following rules will be applied:

37/125

Previous Medication:

- Start date ≤ Start of study intervention OR
- Start date = Missing

Concomitant Medication:

- End date ≥ Start of study intervention AND (Start date ≤ End of study intervention OR Start date=Missing) OR
- End date = Missing AND (Start date \le End of study intervention OR Start date = Missing)

Table 1 Imputation rules for missing/incomplete start/end dates of medication

	Start Date	End Date
Day missing only	Day = 1	Day = Last day of month
	Day = 1	Day = 31
Month missing	Month = Jan	Month = Dec
	Date = Missing	
Year missing	No imputation	
	if imputed date > date of death:	
All	imputation by date of death	

Concentration for pharmacodynamics/biomarkers:

For calculation of descriptive statistics, values below the lower limit of quantification will be set to half of the lower limit value (LLOQ). BLQ will be reported in participant data listings.

Missing data imputation related to the clinical efficacy questionnaires and efficacy estimands will be described in the corresponding sections.

In all participant data listings, imputed values will be presented, and imputed information will be flagged.

Missing statistics, e.g., when they cannot be calculated, should be presented as "ne" (not estimable). For example, if n=1, the measure of variability (SD) cannot be computed and should be presented as "ne".

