7.1.2 Permanent Discontinuation

In rare instances, it may be necessary for a participant to permanently discontinue (definitive discontinuation) study intervention. If study intervention is definitively discontinued, the participant is encouraged to remain in the study until last safety follow-up (i.e., Week 26). The participant should complete the ET assessments as soon as possible and revert to the same study schedule (Table 1) based on the participant's Day 1 until the Safety follow-up visits are completed (see Section 1.3).

The participant must be withdrawn from study intervention in the event of any of the following:

- Enrollment despite violation of an exclusion criterion which, in the Investigator's, and/or Sponsor's opinion, makes discontinuation of the participant necessary.
- Participation in any other interventional study during the duration of this study for which the Investigator considers discontinuation of the study intervention necessary.
- Occurrence of pregnancy.
- Occurrence of a clinical condition (e.g., SAE, SFI defined severe flare) for which discontinuation is considered necessary by the Investigator and/or the Sponsor/designee.

- Non-compliance to study visits, study intervention etc., judged as significant by the Investigator or Sponsor, e.g., taking CCI of the study intervention doses.
- An unplanned event that necessitates discontinuation of study intervention for more than 4 weeks.
- If a participant is unblinded.

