15.2.2 Serious Adverse Events

The following frequency tables will be prepared for serious TEAEs:

- Incidence of serious TEAEs by SOC and PT (*)
- Incidence of related serious TEAEs by SOC and PT (*)

A listing of SAEs will also be provided with the relevant information with a flag for SAEs with onset outside the on-treatment period.

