15.5 ECG Evaluations

ECG summaries will include all ECG assessments collected at Baseline and during the on-treatment period (Week 8, Week 20, Week 24 and ET). All ECG assessments will be listed, and those collected outside the on-treatment period will be flagged in the listing.

The time windows below will be applied to allocate measurements to analysis visits. Unscheduled ECG measurements will be used for the analysis.

Analysis Visit	Target Day	Window Range
Day 1	1	1
Week 8 Day 57	57	> 1 – 70
Week 20 Day 141	141	71 – 154
Week 24 Day 169	169	≥ 155

The following analyses will be performed for each applicable ECG parameter (RR, PR, QRS, QT, ventricular rate -denoted as HR in what follows-, and QTcF) by cohort and study intervention group:

- Descriptive statistics at Baseline, at each post-baseline time point and changes from baseline at each post-baseline time point
- Frequency (number and percentage) of participants with notable ECG values according to the following categories by analysis visit and during the on-treatment period. (*)
 - \circ HR < 50 bpm, < 40 bpm, < 30 bpm
 - o HR increase from baseline > 20 bpm, > 30 bpm, > 40 bpm
 - o HR decrease from baseline > 20 bpm, > 30 bpm, > 40 bpm
 - \circ PR > 200 ms and > 220 ms
 - o PR increase from baseline > 30 ms
 - \circ QRS > 110 ms
 - \circ QTcF > 450 ms, > 480 ms, > 500 ms
 - With/without concomitant antimalarial (ATC code level 3 = P01B)
 - o QTcF increase from baseline > 30 ms, > 60 ms
 - With/without concomitant antimalarial (ATC code level 3 = P01B)

ECG interpretation (normal, abnormal/not clinically significant, abnormal/clinically significant) will be summarized at Baseline and during the on-treatment period.

A shift table from baseline to the worst on-treatment observation in ECG interpretation (normal, abnormal/not clinically significant, abnormal/clinically significant, missing and total) will also be provided.

Complete ECG profiles will be provided for participants with at least one notable ECG value or one notable ECG increase as defined above. For these participants, all ECG parameter values collected during the study will be provided.

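### The SAP's on-treatment period ends at last contact rather than last dose, so safety values from participants who stopped drug early are labelled on-treatment and no last-dose-based summary stands beside them

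*SAP*

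**What the plan says.** SAP 9.8 defines the period: "The on-treatment period is defined as the time from the first dose of study intervention to the date of last contact". SAP 9.6 takes the date of last contact as the latest of several dates up to data cut-off. These include adverse event start and end dates and "Date for any study assessments". By contrast, SAP 9.9 closes exposure at last dose: "end date is the date of last dose of study intervention".

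Protocol 7.1.2 keeps off-drug participants under observation: "If study intervention is definitively discontinued, the participant is encouraged to remain in the study until last safety follow-up", which is Week 26, on the same visit schedule.

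The period governs most safety output:
- SAP 15.3: worst laboratory grades, shift tables, liver categories and the hepatotoxicity plots.
- SAP 15.4: vital signs.
- SAP 15.5: "ECG summaries will include all ECG assessments collected at Baseline and during the on-treatment period".
- SAP 15.2.2: the SAE listing carries "a flag for SAEs with onset outside the on-treatment period". Sections 15.4 and 15.5 ask for similar flags.

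For concomitant medication, SAP 12 uses the on-treatment period and refers to 9.10 for the derivation. The rule in 9.10 instead requires "Start date ≤ End of study intervention OR Start date=Missing".

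**The concern.** A reader of a worst on-treatment table expects values obtained on drug or shortly after it. Here the label carries no such meaning, because every assessment after the first dose, up to data cut-off, is inside the period by construction. Values from a participant who stopped early and stayed are pooled with on-drug values, and nothing in the visible SAP separates them.

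Grade 3 laboratory abnormalities and QTcF increases are secondary safety endpoints, so this affects how a dose-ranging safety profile is read. Stopping may also be related to the signal. Protocol 8.3.8 withholds drug for listed laboratory abnormalities and ends it when Grade 3 or higher is confirmed without another cause. Recovered values from those participants then enter later by-visit means as on-treatment.

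Separately, a medicine started after last dose but before last contact is concomitant under SAP 12 and not under SAP 9.10.

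**Working it through.** No sample size, power or alpha figure depends on this definition, so there is no planned figure to reproduce.

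**1. Off-drug gap.** Week w falls on Day 7w + 1, and the Week 26 visit is Day 183 (SAP 9.7). Gap = 183 − (7w + 1).

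| Last dose at | Gap to Day 183 |
|---|---|
| Week 2 | 183 − 15 = 168 days (24 weeks) |
| Week 4 | 183 − 29 = 154 days (22 weeks) |
| Week 12 | 183 − 85 = 98 days (14 weeks) |
| Week 20 | 183 − 141 = 42 days (6 weeks) |
| Week 24 (completer) | 183 − 169 = 14 days (2 weeks) |

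**2. Share of on-treatment person-time that is off drug.** Assume a fraction q stops uniformly over Weeks 0 to 24 (mean Week 12) and stays to Week 26, giving 26 − 12 = 14 off-drug weeks each. A fraction L of completers enters the extension study and has no tail.

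Share = [(1 − q)·2·(1 − L) + 14q] / [(1 − q)·(24 + 2(1 − L)) + 26q]

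- q = 10%, L = 0: (1.8 + 1.4)/26 = 12.3%, of which early stoppers give 1.4/26 = 5.4%.
- q = 10%, L = 1: 1.4/24.2 = 5.8%.
- Extremes for q from 5% to 30%: 0.7/24.1 = 2.9% (q = 5%, L = 1) and 5.6/26 = 21.5% (q = 30%, L = 0).

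The only planning figure is the 10% withdrawal rate for Cohort A (Protocol 9.2), used here as a stand-in. The rest of the range is assumed.

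**3. By-visit means.** If a fraction f of those assessed is off drug and the effect has fully gone in them, the reported mean effect is (1 − f) times the true one. With f = 10%, 10% is lost. This assumes that those who stop are typical. If those with the largest changes stop, the loss is greater. Completers' Week 26 values have their own visit label, so this attenuation comes from early stoppers.

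**4. Worst-value tables.** Take a constant background hazard b per week, doubled on drug, with no extension entry. For last dose T and window end E, active incidence is 1 − exp[−(2bT + b(E − T))] and placebo incidence is 1 − exp(−bE), averaged over T. Check: placebo to last contact with b = 0.2% is 1 − exp(−0.002 × 26) = 5.07%. The hazards and the doubling are illustrative.

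| q, b | Window ends at | Active | Placebo | Risk difference | Risk ratio |
|---|---|---|---|---|---|
| 10%, 0.2% | last dose | 8.70% | 4.45% | 4.25 | 1.954 |
| | last dose + 2 weeks | 9.07% | 4.84% | 4.23 | 1.875 |
| | last contact | 9.30% | 5.07% | 4.23 | 1.834 |
| 10%, 1% | last dose | 36.37% | 20.31% | 16.05 | 1.790 |
| | last dose + 2 weeks | 37.63% | 21.89% | 15.74 | 1.719 |
| | last contact | 38.56% | 22.89% | 15.66 | 1.684 |
| 30%, 0.2% | last dose | 7.80% | 3.99% | 3.81 | 1.956 |
| | last dose + 2 weeks | 8.17% | 4.37% | 3.80 | 1.869 |
| | last contact | 8.85% | 5.07% | 3.79 | 1.747 |
| 30%, 1% | last dose | 32.86% | 18.26% | 14.59 | 1.799 |
| | last dose + 2 weeks | 34.19% | 19.88% | 14.31 | 1.719 |
| | last contact | 36.98% | 22.89% | 14.08 | 1.615 |

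Incidence rises in both arms, the risk ratio moves toward 1, and the risk difference moves by at most 14.59 − 14.08 = 0.51 points.

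**The case against.** The strongest reply is that the window is prespecified. Protocol section 3, repeated in SAP section 5, sets Day 1 to the end of Safety Follow-up for adverse events, Grade 3 laboratory abnormalities and QTcF increases alike. A reader might conclude that the period should simply be cut near last dose. That would truncate all three endpoints for early stoppers, so the objection stands against replacing the window. It does not justify the name. Protocol 9.4.2.2 speaks of worst on-treatment laboratory values and 9.4.2.4 of ECG change to the end of the treatment period, and neither phrase suggests last contact.

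The exposure is also limited:
- Completers are about 2 weeks off drug at most, and participants entering the extension study have essentially no tail.
- The schedule has no Week 26 ECG, so off-drug ECGs come essentially from early stoppers.
- The Cohort A primary analysis drops data after Week 16 other than adverse events and exposure (SAP 9.1).
- Protocol 7.1.2 calls permanent discontinuation rare, and people who leave the study supply no later values.

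All of this stands and limits the size. It does not help a reader identify the off-drug values that remain.

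The flags are not empty either. Adverse events are recorded from consent, and vital signs and ECGs are taken at Screening, so pre-dose records would be flagged. What the flags cannot do is mark any off-drug value.

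**Conclusion.** The definition should be corrected, though the numerical effect is modest. The labelling problem follows from SAP 9.6 and 9.8 together and needs no assumption. The attenuation of by-visit means (about 10% if 10% are off drug and still attending) and of risk ratios (1.954 to 1.834 in the low-hazard 10% case) rests on assumed discontinuation and hazards. Selective or unequal stopping between arms could enlarge it or change its direction, which the documents do not allow to be quantified.

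Three stronger readings are not supported:
- That drug effects are diluted throughout the safety output. A longer window cannot hide an on-drug abnormality; worst-value counts can only rise and risk differences hardly move.
- That a stated number of milliseconds of QTcF effect is lost. The documents give no expected QTcF effect.
- That late events cannot be drug-related. The documents give no half-life or time to offset of effect.

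The conflict between SAP 12 and SAP 9.10 on concomitant medication is a plain inconsistency, whatever the bias.

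**What to change.** 1. Rename the current SAP 9.8 period on-study and keep it for the protocol safety endpoints: adverse events including serious events and those of special interest, Grade 3 laboratory abnormalities and QTcF increases. Carry the new name through wherever the SAP uses the old one.
2. Define on-treatment as first dose to last dose plus a residual window justified by the sponsor. Fourteen days, the length of the safety follow-up, is one candidate, but the documents do not tie it to the drug's elimination.
3. Report the laboratory, liver, ECG and vital-sign summaries and one overview of treatment-emergent adverse events for that period, next to the on-study versions. Flag later values in the listings.
4. Reconcile SAP 12 with SAP 9.10, so that one end date decides whether a medicine is concomitant.

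The cost is SAP wording, one derived flag and some repeated tables. The restricted tables will hold slightly fewer values at late visits and will leave out values after a safety-driven stop, so they should supplement the on-study tables and not replace them.

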9.11 Scoring and Handling of Missing Item-level Data for Clinician-Reported Outcomes

9.11.1 CLASI

Cutaneous Lupus Erythematosus Disease Area and Severity Index (CLASI) is a validated measurement instrument for lupus erythematosus developed for use in clinical studies that consists of 2 separate scores evaluating disease activity (CLASI-A) and damage (CLASI-D). The activity scale includes measurements of erythema, scale /hypertrophy, active alopecia, recent hair loss and mucous membrane disease, whereas the damage scale measure dyspigmentation, atrophy, and scarring.

Scores range from 0 to 70 points for CLASI-A total score. Mild, moderate, and severe disease corresponds to CLASI activity score ranges of 0 to 9, 10 to 20, and 21 to 70, respectively.

The CLASI-A total score as collected in eCRF will be used in the analysis. Sub-scores will be computed using individual items. Erythema sub-score will be computed as the sum of scores obtained after rating of erythema for each of the 13 body areas. Scale/hypertrophy sub-score will be computed as the sum of scores obtained after rating of scale/hypertrophy for each of the 13 body areas. Erythema sub-score ranges from 0 to 39. Scale/hypertrophy sub-score ranges from 0 to 26.

9.11.3 BILAG 2004

The BILAG 2004 Disease Activity Index evaluates SLE activity in a number of 9 organs or systems.

A separate alphabetic score is assigned to the 9 organs or systems, corresponding in general to the following definitions:

- BILAG A: Severe disease activity requiring any of the following treatments (e.g., systemic high dose oral CS, intravenous pulse CS, systemic immunosuppressants, or therapeutic high dose anticoagulation in the presence of high dose CS or ≥ 20 mg prednisone).
- BILAG B: Moderate disease activity requiring treatment with systemic low-dose oral glucocorticoids, intramuscular or intra-articular or soft tissue CS injection, topical CS or immunosuppressants, or symptomatic therapy such as antimalarials or NSAIDs
- BILAG C: Mild disease
- BILAG D: System previously affected but now inactive
- BILAG E: System never involved

The BILAG 2004 is evaluated by scoring each of a list of signs and symptom as: improving (1); same (2); worse (3); new (4); not present (0); not done (nd). For some items, appropriate responses may be: Y/N or numerical values where indicated, or Y/N confirm this is due to SLE activity.

The grade scoring for each organ domain is provided in appendix 18.1.1.

Handling of missing items:

Single imputation will be done at the item level unless the questionnaire is ticked as Not done. For all organ domains, missing items (including 'Not done') will be imputed using the value carried forward from the preceding analysis visit (only value observed after Baseline can be used for imputation and no imputation can be done from a value previously imputed itself).

results may only be available as per Investigator's opinion. If not available, they are not considered as missing, but as not applicable and will not be imputed. This applies to items 95, 96 and 97 from the hematological domain (respectively thrombotic thrombocytopenic purpura [TTP], evidence of active hemolysis and Coombs' test positive).

If after imputation of missing items, the score cannot be assigned to the organ or system at the visit, then it will be considered as missing.

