BILAG Flare

Use of the BILAG index for evaluating flares has been identified as a meaningful way of evaluating the efficacy of drugs; this judgment has been corroborated by external advisors and regulatory authorities.

BILAG assessments should be conducted by a trained evaluator.

The BILAG index flare definition were used in the SLICC Flare study in May 2009 published in Annals of Rheumatic Diseases (Isenberg 2011).

On the participant level:

- 1. A severe flare is defined as at least one BILAG A score in any organ systems due to one or more items that are new or worse*, in the month leading up to the current visit, compared to the patient's condition during the previous month
- 2. A moderate flare is defined as at least 2 BILAG B organ scores due to items that are new or worse* in the moth leading up to the current visit previous month, when the participant does not meet the criteria for the severe flare
- 3. A mild flare is defined as one single BILAG B score in any organ systems due to items that are new or worse* in the month leading up to the current visit, compared to previous month, or at least 3 BILAG C scores in any organ systems due to items that are new or worse
- 4. No flare is defined as without meeting any of these criteria.

Investigators will be trained to score worse only if there is significant deterioration compared to the prior month and to score new only when the item was not present in the prior month according to the BILAG glossary. In organs (renal and hematological) in which an A, B, or C score depend on whether or not laboratory results are attributed to SLE, Investigators will be queried to ensure that there is medical justification for this decision.

A copy of the BILAG 2004 and glossary is provided in the Investigator portal.

SLEDAI Flare Index

The SFI can be used with any version of the SLEDAI and will be used with the CCI for the purposes of this trial.

[figure not shown]
A mild/moderate flare is defined as any of the following:

•	Increase in SLEDAI instrument score of	of 3 po	oints or more ((but total	score not to	more than	12)
---	--	---------	-----------------	------------	--------------	-----------	-----

A severe flare is defined as any of the following:

• Increase in SLEDAI instrument score leading to total score > 12.

[figure not shown]
^{*}On the organ system level:

Patient-Reported Assessments

Functional Assessment of Chronic Illness Therapy-Fatigue

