A moderate flare is defined as at least two BILAG B organ scores due to items that are new or worse* in the month leading up to the current visit, when the participant does not meet the criteria for the severe flare.

A severe flare is defined as at least one BILAG A score in any organ systems due to one or more items that are new or worse*, in the month leading up to the current visit, compared to the participant's condition during the previous month.

[figure not shown]
*"Items that are new or worse" means that if the assigned grade A/B or C contains any item which is WORSE or NEW, such grade will be included into the flare consideration. This is valid for clinical organ domains. For laboratory organ domains (i.e., renal and hematological) where items are not classified as worse or new, there has to be an increase in score from B to A or C to B for flare to be considered.

All post-baseline BILAG assessments until Week 24 will be considered.

Time to first moderate/severe BILAG flare (weeks) will be derived as follows:

Time to first moderate/severe BILAG flare
= [min(Dates of visit with moderate/severe BILAG flare) - Date of randomization + 1]/7
The following censoring rules will be applied:

- Participants discontinuing the study prior to Week 24 without moderate/severe flare will have their time to first moderate/severe flare censored at the last visit at which flare could have been assessed (i.e., date of last BILAG assessment). Participants discontinuing the study prior to any post-baseline assessments will be censored at randomization date.
- Participants completing the 24-week treatment period without moderate/severe flare will have their time to first moderate/severe flare censored at Week 24.

Each stratum will define a separate baseline hazard function, i.e., for the i-th stratum the hazard function is expressed as: $h(i;t) = h(i,0;t) \exp(x\beta)$, where h(i,0;t) defines the baseline hazard function for the i-th stratum and x defines the study intervention group and β is the unknown regression parameter. Ties will be handled by replacing the proportional hazards model by the discrete logistic model.

The one-sided p-value from the stratified log rank test will be reported. This p-value should be considered as exploratory.

Results from an unstratified analysis will also be provided (HR together with its 95% CI and one-sided p-value from log rank test).

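### Carrying BILAG change scores forward repeats 'new' or 'worse' at a visit where the item was not assessed and can, in a narrow set of cases, create a first moderate flare that was never observed

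*SAP*

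**What the plan says.** **Scoring.** SAP 9.11.3 codes BILAG items as "improving (1); same (2); worse (3); new (4); not present (0); not done (nd").

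**Missing items.** The same section states that, in every organ domain, "missing items (including 'Not done') will be imputed using the value carried forward from the preceding analysis visit". Scores 3 and 4 are neither exempted nor recoded to 2. Three limits apply: "Single imputation will be done at the item level unless the questionnaire is ticked as Not done"; "only value observed after Baseline can be used for imputation and no imputation can be done from a value previously imputed itself"; and three hematological items (95, 96 and 97) are exempt.

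**Meaning of the scores.** Protocol Appendix 8 (BILAG Flare) has investigators trained to score worse only on significant deterioration from the prior month and to "score new only when the item was not present in the prior month according to the BILAG glossary".

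**Flare.** Under SAP 14.3.11 a moderate flare needs "at least two BILAG B organ scores due to items that are new or worse* in the month leading up to the current visit", and a severe flare needs one such A score. In clinical domains, "if the assigned grade A/B or C contains any item which is WORSE or NEW, such grade will be included into the flare consideration". Renal and hematological domains instead need a rise in grade. The derivation takes every post-baseline BILAG assessment to Week 24 and says nothing about imputed items.

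**The concern.** Carry-forward is defensible for a level, because the last known state may well persist. It fits a change score poorly. Repeating 'same' is harmless. Repeating 'new' or 'worse' reports a fresh event in a month for which there is no information.

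The moderate-flare rule is a threshold of two B scores at one visit. One carried score can therefore complete the pair. Because the endpoint is time to first moderate/severe flare, such an event also ends that participant's time at risk. At stake is the integrity of individual flare events in one Cohort B secondary endpoint.

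**Working it through.** **1. The rules side by side**

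| Score at preceding visit | Imputed at missing visit | Against Protocol Appendix 8 |
|---|---|---|
| 4 (new) | 4 | Not allowed: the item was recorded as present at the preceding visit |
| 3 (worse) | 3 | Possible in principle, but a second deterioration that was not assessed |
| 0, 1 or 2 | same value | Does not make a grade flare-qualifying |

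**2. Where it can act.** Protocol Table 1 schedules BILAG at Weeks 4, 8, 12, 16, 20 and 24 after Day 1. Week 4 has no post-baseline donor value, so five visits (Weeks 8 to 24) are exposed. SAP 9.11.3 has nine organ systems. Two (renal, hematological) need a grade increase, which leaves 9 − 2 = 7 clinical domains.

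**3. Enumeration.** Take two clinical domains and two consecutive post-baseline visits. Each domain is none, B through a worse/new item, or A through a worse/new item, and at least one domain is missing at the second visit. There are 3 × 3 = 9 first-visit patterns. There are 3 + 3 + 1 = 7 second-visit patterns (either domain missing, or both). That gives 63 in all.

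- In 24 of 63, the second-visit flare exists only through the carried value.
- In 22 of these 24, a flare was already observed at the first visit, so time to first flare is unchanged.
- In 2, a first flare is created.

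The two are mirror images. For example, at Week 8 domain 1 has a B through a new item and domain 2 has none, so there is no moderate flare. At Week 12 the domain 1 item is missing and carried forward as new, and domain 2 shows its first new B. The rules count two B scores, yet two were never observed together. If imputed items cannot qualify a grade, the 24 and the 2 both fall to 0.

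**4. Illustrative size.** The documents give no item-missingness or flare rate, so every input here is assumed: 3 clinical domains, 6 visits, independent probability p of a worse/new B per domain and visit, and a fraction m of items missing. Severe flares are left out.

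- Chance of two or more B scores at a visit: q = 3p²(1 − p) + p³.
- Participants with an event over six visits: F = 1 − (1 − q)⁶.
- For observed items only, replace p by p(1 − m).

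With p = 0.08: q = 0.017664 + 0.000512 = 0.018176, F = 10.4%. With m = 0.10, p(1 − m) = 0.072, q = 0.014805, F = 8.6%.

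With p = 0.05: q = 0.00725, F = 4.3%. With m = 0.10, p(1 − m) = 0.045, q = 0.005893, F = 3.5%.

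The current rule was simulated:

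| p | m | Nothing missing | Current rule | Observed items only | First event only through carry-forward |
|---|---|---|---|---|---|
| 5% | 10% | 4.3% | 4.0% | 3.5% | 0.53% |
| 8% | 10% | 10.4% | 9.7% | 8.6% | 1.18% |

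At m = 2% the last column is 0.12% (p = 5%) and 0.27% (p = 8%). At m = 5% it is 0.29% and 0.63%. The span is about 0.1 to 1.2% of participants. About 90% of the events that carry-forward adds are false in this model. Observed-only counting adds none.

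A wider set of assumptions (7 domains, p from 2 to 10%, A score 0.5%, m from 1 to 10%) gives a flare event without any true flare in 0.05 to 1.9% of participants. A first flare is created or moved earlier, compared with observed items only, in 0.06 to 4.1%.

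**5. Treatment comparison.** If one arm has p = 5% and the other 8%, the ratio of per-visit flare probabilities is 0.00725/0.018176 = 0.399 with nothing missing. With observed items only at m = 10% it is 0.005893/0.014805 = 0.398. A simulated hazard ratio was 0.400 with nothing missing, 0.401 under the current rule and 0.398 with observed items only.

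**The case against.** **SAP 14.3.11 never cites 9.11.** Where item imputation feeds an endpoint, the SAP says so for BICLA (14.2.3), SRI-4 (14.3.6) and remission (14.3.8). That imputed items enter the flare derivation is therefore an inference. It is the natural one, because 9.11.3 is a general scoring rule for all domains with its own listed exemptions and flare is not among them. If observed items only were intended, the SAP should say so.

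**Part of the text is not visible.** The public copy of 9.11.3 has a gap after the imputation rule, and the organ grading rules in Appendix 18.1.1 are not shown. Whether one carried item is enough for a B in a given domain, or could lift a domain to A, cannot be checked. This stands as a limit.

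**A reader might infer that both carried scores are forbidden.** Only the carried 4 contradicts Appendix 8. A worse followed by a worse is a legitimate sequence; the difficulty is that it was not assessed.

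**A reader might infer that no flare occurred in the example.** The documents do not support that. The domain 1 item was not assessed and may have worsened, so its status is undetermined. Refusing to count imputed items is itself a form of single imputation: it treats every unassessed item as not deteriorated.

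**The change moves the total flare rate further from the truth.** This is correct in the model: 10.4% true, 9.7% under the current rule, 8.6% with observed items only. The current rule comes closer because false events partly offset flares hidden by missing items. That is not a reason to assign events to the wrong participants, but the cost must be stated.

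**Conclusion.** The point holds as a narrow inconsistency between the imputation rule and the flare definition. As written, the rules can create a first moderate flare that was never observed. The exposure is confined to isolated missing items in clinical domains at Weeks 8 to 24. The bars on baseline donors, chained imputation and imputing a form that was not done all limit it, as does the grade-increase rule for renal and hematological domains. Severe flares are rarely affected, because the A score would normally have counted at the earlier visit.

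The size in this trial is unknown. The range of about 0.1 to 1.2% of participants rests wholly on assumed incidence, missingness and independence, and could be negligible if few items are missing. Dividing by the moderate flares in the model gives a more striking share (1.18/9.7 = 12% in the last table row). That figure should not be used for the endpoint, whose denominator also includes severe flares.

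A reader might also infer a biased treatment effect or an effect on the primary test. Neither is supported. The trial is double-blind, the illustrative hazard ratio barely moves, and the problem lies in the flare derivation, not in BICLA. Protocol 9.4 treats secondary p-values as nominal, and SAP 14.3.11 labels this log-rank p-value exploratory.

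**What to change.** 1. Leave 9.11.3 as it is for organ grading, so that BICLA and SRI-4 do not change.
2. Add to 14.3.11 that, in the clinical domains, only items actually scored 3 or 4 at the visit in question can make a grade flare-qualifying, and that an imputed item never counts as new or worse.
3. Report, by study intervention group, the number of first moderate/severe flares that would depend on an imputed item. This shows the size in the real data.
4. State the downside: flares hidden by unassessed items are missed, so the absolute flare rate is undercounted slightly more than under the current rule.

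The cost is a sentence or two in the SAP, one condition in the flare program and one extra count. No new data are needed.
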